10.2.3.1. Definitions of Adverse Events

An AE is any untoward medical occurrence in a patient or clinical investigation subject administered a pharmaceutical product and which does not necessarily have to have a causal relationship with this treatment.

Therefore, an AE can be any unfavorable and unintended sign (including an abnormal laboratory finding, for example), symptom, or disease temporally associated with the use of a medicinal product, whether or not considered related to the medicinal product.

An AE includes, but is not limited to, the following:

Any clinically significant worsening of a pre-existing condition other than CM is considered to be an AE. However, worsening of CM is considered to be "disease progression" or "lack of efficacy" and need not be reported as an AE unless it or the signs and symptoms associated with CM are more severe than expected for the subject's condition.

An AE occurring from overdose (i.e., a dose higher than that indicated in the protocol) of a study drug, whether accidental or intentional.

The criteria for determining whether an abnormal objective test finding should be reported as an AE are as follows:

- Test result is associated with accompanying symptoms
- Test result requires additional diagnostic testing
- Test result requires significant additional concomitant drug treatment, or other therapy or intervention
- Test result leads to a change in trial dosing or discontinuation of study drug
- Test result is considered to be an AE by the Investigator or Sponsor

Merely repeating an abnormal test, in the absence of any of the above conditions, does not constitute an AE. Any abnormal test result that is determined to be an error does not require reporting as an AE.

A clinical diagnosis, rather than the changes in laboratory or other assessment should be recorded on the eCRF as appropriate (e.g., anemia versus low hemoglobin value, bundle branch block rather than abnormal electrocardiogram (ECG)).

For Cohorts 1 to 9, from the time the subject receives the single administration (or initial for repeat) study treatment until 30 days after the subject completes the study treatment, protocol-related events should be recorded as well. For Cohort 10, 11 and 12 subjects, these should be recorded until the last study visit for the subject. A protocol-related AE is an AE occurring during a clinical study that is not related to the study product, but is considered by the Investigator or medical monitor to be related to the research conditions. For example, a protocol-related AE may be an event related to a medical procedure required by the protocol.

10.2.3.2. Serious Adverse Events

Any adverse experience occurring at any dose that results in any of the following outcomes is classified as a serious adverse event (SAE).

- Results in death
- Life threatening (see below for definition)
- Results in persistent or significant disability/incapacity (see below for definition)
- Requires subject hospitalization or prolongs subject hospitalization (see below for definition)
- Results in a congenital anomaly/birth defect in a neonate/infant

Additionally, important medical events that may not result in death, be life-threatening, or require hospitalization may be considered serious AEs when, based on appropriate medical judgment, they may jeopardize the subject and may require medical or surgical intervention to prevent one of the outcomes listed in this definition. Examples of such events include allergic bronchospasm requiring intensive treatment in an emergency room or at home, blood dyscrasias or convulsions that do not result in hospitalization, or development of drug dependency or drug abuse.

Life-threatening refers to immediate risk of death as the event occurred per the reporter. A life-threatening experience does not include an experience, had it occurred in a more severe form, might have caused death, but as it actually occurred, did not create an immediate risk of death.

For example, an allergic reaction resulting in angioedema of the face would not be life threatening, even though angioedema of the larynx, allergic bronchospasm, or anaphylaxis can be fatal.

Hospitalization is official admission to a hospital. Hospitalization or prolongation of a hospitalization constitutes criteria for an AE to be serious; however, it is not in itself considered a SAE. In the absence of an AE, a hospitalization or prolongation of a hospitalization should not be reported by the PI. This is the case in the following situations:

- The hospitalization or prolongation of hospitalization is part of a routine procedure followed by the center (e.g., stent removal after surgery, or other elective procedures). This should be recorded in the study file.
- Hospitalization for survey visits or annual physicals falls in the same category.

Disability is defined as a substantial disruption in a person's ability to conduct normal life functions.

10.2.3.3. Adverse Event Recording and Reporting

Serious Adverse Events (SAEs) should be reported from the time the subject signs the informed consent to 30 days after the subject completes the study treatment. Adverse Events (AE) should be reported from the time the subject receives the single Light-activated AU-011 administration (or initial for repeat) study treatment to 30 days after the subject completes the study treatment. After 30 days, for Cohorts 1 to 9, only AEs or SAEs determined by the Investigator to be related to study product and/or study procedures are to be reported. Relatedness to Light-activated AU-011 treatment and/or study procedures is determined by the Investigator. For Cohort 10, 11 and 12 subjects, all SAEs and AEs will be reported from the time the subject signs the informed consent through their last study visit. All AEs, regardless of severity and whether or not they are ascribed to the study treatment, will be recorded in the source documents. All AEs and SAEs for subjects who are not screen failures will be recorded on the eCRF.

Study Investigators must follow-up on all AEs, SAEs, and other reportable events until the events have resolved, returned to baseline, or in case of permanent impairment, until the condition stabilizes. If, in the opinion of the Investigator, the AE or laboratory abnormality/ies are not likely to improve because of the underlying disease, the Investigator must record his or her reasoning for this decision in the subject's source documentation and on the eCRF. Any medication or other intervention necessary for the treatment of an AE must be recorded on the concomitant medication eCRF.

All AEs will be characterized by the following criteria:

- Event term
- Intensity or severity
- Relationship to study treatment
- Outcome
- Treatment or action taken.

Whenever possible, recognized medical terms should be used when recording AEs. Colloquialisms and/or abbreviations should not be used.

If more than one distinct AE occurs, each event should be recorded separately. However, if known at the time of reporting, a diagnosis (i.e., disease or syndrome) should be recorded on the eCRF rather than individual signs and symptoms (e.g., record congestive heart failure rather than dyspnea, rales, and cyanosis). However, if a constellation of signs and/or symptoms cannot be medically characterized as a single diagnosis or syndrome at the time of reporting, each individual event should be recorded as a separate AE. A diagnosis that is subsequently established should be reported as follow-up information. However, signs and symptoms that are considered unrelated to an encountered syndrome or disease should be recorded as individual AEs (e.g., if congestive heart failure and severe headache are observed at the same time, each event should be recorded as an individual AE).

AEs occurring secondary to other events (e.g., sequelae) should be identified by the primary cause; a "primary" event, if clearly identifiable, should represent the most accurate clinical term to record as the AE event term. For example:

Orthostatic hypotension → fainting and fall to floor → head trauma → neck pain

The primary event is orthostatic hypotension and the sequelae are fainting, fall, head trauma and neck pain.

10.2.3.4. Classification of Adverse Events by Intensity/Severity

All AEs should be graded by Investigators using the Common Terminology Criteria for Adverse Events (CTCAE) version 4.03 (Appendix 3). If the AE is not specifically listed in the CTC toxicity criteria (for instance posterior segment inflammation, as opposed to uveitis), use the following grades:

- Grade 1: Mild; asymptomatic or mild symptoms; clinical or diagnostic observations only; intervention not indicated.
- Grade 2: Moderate; minimal, local or noninvasive intervention indicated; limiting age-appropriate instrumental Activities of Daily Living (ADL)
 - Instrumental ADL refer to preparing meals, shopping for groceries or clothes, using the telephone, managing money, etc.
- Grade 3: Severe or medically significant but not immediately life-threatening; hospitalization or prolongation of hospitalization indicated; disabling; limiting self-care ADL.
 - Self-care ADL refer to bathing, dressing and undressing, feeding self, using the toilet, taking medications, and not bedridden
- Grade 4: Life-threatening consequences; urgent intervention indicated
- Grade 5: Death related to AE

There is a distinction between the severity and the seriousness of an AE. Severity is a measurement of intensity; thus, a severe reaction is not necessarily a SAE. For example, a

headache may be severe in intensity, but would not be serious unless it met one of the criteria for SAEs.

Expectedness

All AEs considered related to Light-activated AU-011 will be evaluated as to whether they are expected or unexpected, and related to Light-activated AU-011, the laser, and/or both. Expectedness will be determined by the Sponsor.

Expected (anticipated): An AE is expected when the nature, severity, or degree of incidence was previously described in the IB.

Unexpected (unanticipated): An AE is unexpected when the nature, severity, or degree of incidence was not previously described in the IB.

Relatedness

The Investigator will determine the assessment of the causal relationship of the AE to the study product and/or laser treatment. The following terms for assessment of the causality to study product or study procedures are to be used:

- Not related: An event that does not follow a reasonable temporal sequence from administration of the study product or procedure, does not follow a known or expected response pattern to the suspect product or procedure and that could be reasonably explained by the known characteristics of the subject's clinical state.
- Related: An event that follows a reasonable temporal sequence from administration of the study product or procedure, follows a known or expected response pattern to the suspected product or procedure and that could not be reasonably explained by the known characteristics of the subject's clinical state.

Outcome

The clinical outcome of an AE will be characterized as follows:

- Ongoing
- Resolved
- Resolved with sequelae
- Death
- Unknown

Action Taken with Study Drug or Procedure

- None
- Study product or procedure interrupted
- Study product or procedure discontinued

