8.4. Dose Escalation Design and Toxicity

8.4.1. DLT Definition

Dose limiting toxicity[ies] (DLT[s]) is defined as a treatment-related safety event (related to drug and/or laser), severe enough to limit dose escalation (increase of dose or frequency of dosing) of AU-011.

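### The two causality definitions cover only 2 of 8 event patterns, and new or confounded toxicity fits neither, so it may be left out of related-event counts and of late reporting in Cohorts 1–9

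*Protocol*

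**What the plan says.** **Causality (Protocol 10.2.3.4, Relatedness).** The decision is the Investigator's: "The Investigator will determine the assessment of the causal relationship of the AE to the study product and/or laser treatment". There are two terms, each with three conditions joined by *and*.

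- Related: the timing is reasonable, and the event "follows a known or expected response pattern to the suspected product or procedure and that could not be reasonably explained by the known characteristics" (meaning the subject's clinical condition).
- Not related: the timing is not reasonable, and the event "does not follow a known or expected response pattern to the suspect product or procedure and that could be reasonably explained by the known characteristics" (again meaning the clinical condition).

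**Expectedness (same section).** "All AEs considered related to Light-activated AU-011 will be evaluated as to whether they are expected or unexpected". The Sponsor makes this call against the IB: "An AE is expected when the nature, severity, or degree of incidence was previously described in the IB". The definition of an unexpected event uses the same list, also joined by *or*, in the negative.

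**Where the Related call is used.**

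- Protocol 8.4.1 defines a DLT as "a treatment-related safety event (related to drug and/or laser), severe enough to limit dose escalation".
- Protocol 10.2.3.3 says that in Cohorts 1 to 9, once 30 days have passed, "only AEs or SAEs determined by the Investigator to be related to study product and/or study procedures are to be reported". The visit instructions from Week 12 to Week 104 and footnote h of Appendix 1 follow that rule. Cohorts 10 to 12 report everything to the last visit.
- SAP 9.3 and 9.4 plan separate tables of related TEAEs and related SAEs. SAP 9.3 counts a missing relationship as related.

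**A conflicting instruction.** Protocol 10.2.3.3 also requires every AE in source documents whatever its cause, and says that all AEs and SAEs of subjects who are not screen failures go on the eCRF. That last sentence has no limit by time or relatedness.

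**The concern.** The primary objective is safety, and the product is new. Two kinds of event matter most: a reaction not seen before, and a change in the treated eye that either the treatment or the melanoma could have caused. Read literally, neither can be Related. The first has no known or expected pattern yet, and the second has a reasonable explanation in the subject's clinical state.

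This sits badly with the expectedness step, which presupposes that some related events are unexpected. If Related already requires a known or expected pattern, an event of a new kind cannot reach that step.

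Three uses of the label depend on a positive Related call: DLT status, the related-event tables, and reporting after 30 days in Cohorts 1–9. Failing the Not related definition therefore gives no protection. An unclassified event enters these uses only if the Investigator calls it Related against the wording or, for the tables, if causality is left blank on a recorded event.

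**Working it through.** The plan gives no figure to reproduce. Three checks follow.

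**1. Are the two definitions exhaustive?** Three yes/no conditions give 2 × 2 × 2 = 8 combinations.

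| Timing reasonable | Known or expected pattern | Explained by clinical state | Term met |
|---|---|---|---|
| yes | yes | no | Related |
| yes | yes | yes | neither (confounded event) |
| yes | no | no | neither (new event) |
| yes | no | yes | neither |
| no | yes | yes | neither |
| no | yes | no | neither |
| no | no | yes | Not related |
| no | no | no | neither |

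Two combinations are covered and six are not. These are logical cells, not frequencies.

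**2. How much follow-up is under the related-only rule?** Inputs: last planned dose on Day 1, 8 or 15; all-cause reporting for 30 days afterwards (Protocol 10.2.3.3); any AE still recorded at Week 6 in the two- and three-dose cohorts and at Week 8 in the three-dose cohorts (Protocol 10.1.10 and 10.1.11); target days 43, 57 and 728 for Weeks 6, 8 and 104 (SAP 11.2). Share = (728 − last all-cause day) / 728.

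- Single dose: 1 + 30 = Day 31; (728 − 31)/728 = 697/728 = 95.7%.
- Two doses: 8 + 30 = Day 38, extended to Day 43 by Week 6; (728 − 43)/728 = 685/728 = 94.1%.
- Three doses: 15 + 30 = Day 45, extended to Day 57 by Week 8; (728 − 57)/728 = 671/728 = 92.2%.

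The range is about 92–96%. SAP 4.2 records early termination with final analysis after Week 52. For a subject followed only to Week 52 (target Day 365), the share runs from (365 − 57)/365 = 84.4% to (365 − 31)/365 = 91.5%. A subject given further AU-011 has a lower share, because Appendix 4 reopens all-AE recording through four weeks after that treatment.

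Subjects concerned: Cohorts 1–8 at 3 each plus up to 12 in Cohort 9 = 8 × 3 + 12 = 36. The cohort maxima total 36 + 6 + 6 + 15 = 63 (the plan says approximately 60), so 36/63 = 57%. This assumes that Cohort 9 fills and no cohort is expanded for a DLT.

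**3. Are Expected and Unexpected exclusive?** Take an event whose nature is in the IB but whose severity is not. It is Expected, because one listed attribute is described. It is also Unexpected, because another is not. The categories overlap.

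**The case against.** A reader might infer that new or confounded toxicity is by definition unrelated, and that after 30 days in Cohorts 1–9 it is never reported. The documents do not support that.

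- Such events fail Not related as well. A well-timed new reaction has neither the missing timing nor the clinical explanation that the term requires. The text leaves the choice to the Investigator, who may still call the event Related. A bias towards fewer related events is plausible but does not follow from the wording alone.
- Protocol 10.2.3.3 keeps every AE in source documents and, in one sentence, on the eCRF. If causality is left blank on a recorded event, the SAP counts it as related.
- BCVA, slit lamp, IOP, fundoscopy, fundus photographs and EDI-OCT continue to Week 104, and SAP 8.2 and 9.6 summarise visual acuity, slit lamp, IOP and fundoscopy findings whatever the cause. Objective study-eye changes are not lost, though their AE classification may be.
- The stated escalation reviews fall between one day and four weeks after treatment, inside the all-cause window. The medical monitor and independent ocular oncologist review AEs and DLT determinations together. The SAP also tabulates all TEAEs.
- Relatedness is the Investigator's judgement of a response pattern, and expectedness is the Sponsor's comparison with the IB. A recognised reaction of unlisted severity can be both Related and Unexpected, so the two rules are not flatly contradictory. No SAP table uses expectedness.

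These points limit the consequence. They do not repair the definitions. The eCRF sentence conflicts with the related-only sentence in its own section, and the visit-by-visit instructions follow the related-only one. An event held only in source documents does not reach the tables, and the SAP's missing-means-related rule works only on recorded events.

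**Conclusion.** The point holds in this form. The causality definitions are not exhaustive (2 of 8 combinations covered), and Related requires both a known or expected pattern and no other reasonable explanation. New or confounded toxicity fits neither term, and its class depends on a choice that the text does not guide. Such events may be left out of DLT and related-event counts and, in Cohorts 1–9, may go unreported late.

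The exposure to the rule is about 92–96% of one-cycle follow-up to Week 104 for 36 planned subjects, on the assumptions of target visit days, no further AU-011 and no cohort expansion. This is a share of days, not of events. The number of events misclassified or missed cannot be derived from the documents.

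**What to change.** In Protocol 10.2.3.4:

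- Define Related as a reasonable possibility that drug, injection or laser caused or contributed to the event, and delete the requirement for a known or expected pattern.
- Define Not related as the absence of such a possibility, and record as Related any event that the Investigator cannot place. All eight combinations then have a term.
- Make Expected and Unexpected mutually exclusive, for instance by requiring nature, severity and incidence all to be described in the IB for Expected.

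In Protocol 10.2.3.3, reconcile the related-only sentence with the sentence that puts all AEs and SAEs on the eCRF, and align the visit instructions and Appendix 1 with the result.

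Do not re-adjudicate events already recorded. SAP v5.0 was written after the first database lock, and revisiting causality in an open-label trial at that stage could bring a bias of its own. Instead, state in the study report which causality definition applied, and give all-cause TEAEs equal prominence with related TEAEs.

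The cost is protocol wording, a memo to sites and a paragraph in the report; the all-cause tables are already planned. Related-event rates will look somewhat less favourable, because the default moves doubtful events into Related. With the study terminated early, the report statement is the part most likely to affect how these results are read.

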10.2.3.5. Serious Adverse Event Reporting

Serious Adverse Events (SAE) must be reported to the Sponsor as soon as possible and no later than 24 hours after the Investigator first learns of the event. The SAE form is to be completed

and submitted by email to Aura Biosciences. For initial reports, Investigators should record all case details that can be gathered within the reporting timeframe. Relevant follow-up information should be submitted to the Sponsor as soon as it becomes available and/or upon request. For some events, the Sponsor or designee or the medical monitor may follow up with the site by telephone, fax, electronic mail, and/or a monitoring visit to obtain additional case details deemed necessary to appropriately evaluate the event (e.g., hospital discharge summary, consultant report, or autopsy report). Reports relating to the subject's subsequent medical course must be submitted to the Sponsor until the event has resolved or, in case of permanent impairment, until the event stabilizes and the overall clinical outcome has been ascertained.

SAE reporting timelines should be followed when reporting a pregnancy or symptomatic overdose.

The SAE report should be sent to the medical monitor and Aura Biosciences via e-mail – [contact]. The following contact information (during both business and non-business hours) is also available:

•	Medical Monitor,		:		
•	Aura Biosciences,				
Study personnel are free to contact the medical monitor, by phone at					
, or b	y email at		regarding any	SAE or medical con	icerns.

Transmission of the SAE report should be confirmed by the site personnel submitting the report. Follow-up information for SAEs and information on non-serious AEs that become serious should also be reported to the Sponsor as soon as it is available; these reports should be submitted using the SAE Report Form. Non-serious AEs that become serious should be reported to the Sponsor within 24 hours and recorded on the SAE Report Form.

10.3. Ophthalmic Assessments

10.3.1. Best Corrected Visual Acuity (BCVA)

The study's independent visual acuity consultants will certify the visual acuity equipment, examination rooms, and examiners before the study begins at each site. Manifest refraction and BCVA measurement will be performed according to the standard ETDRS refraction and visual acuity testing protocol in **both eyes at all visits**.

10.3.2. Intraocular Pressure (IOP)

IOP will be measured using applanation or tonopen in the study eye at every study visit and in **both eyes** at Visit 1 (Screening) and Visit 11 (Week 12), and at any Early Termination Visit that occurs before Visit 11 (Week 12). In addition, for all 80 µg dose cohorts, IOP must be 21 mm Hg or less before each injection and before discharge from the clinic.

